#### 6.6.6.1. Hematology

Samples for hematology analyses will be collected prior to IP administration on Day 1 of each treatment cycle, whenever possible. The schedule of hematology assessments for subjects included in the study is as follows:

- During screening
- Cycles 1 and 2 – Days 1, 8, 15 and 22
- Cycles 3 and beyond – Days 1 and 15
- Treatment Discontinuation Visit
- 28-day Follow-up Visit (After discontinuation of subcutaneous azacitidine treatment)
- 90-day Follow-up Visit (Subjects who received durvalumab)

Complete blood count (CBC) for hematology assessment includes:

- Red blood cell count
- Hemoglobin
- Hematocrit
- Reticulocyte count
- Mean corpuscular volume (MCV)
- Red blood cell distribution width (RDW)
- Platelet count
- White blood cell (WBC) count with differential
  - Absolute neutrophils
  - Absolute lymphocytes
  - Absolute monocytes
  - Absolute eosinophils
  - Absolute basophils
  - Percent blasts

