Progressive Diseaseb	Defined as: 1) a > 50% increase in bone marrow blast count percentage from the baseline bone marrow blast count that persists for at least 2 bone marrow assessments separated by at least 1 month, unless the baseline bone marrow blast count is > 70%, in which case, a finding of > 70% blasts that persists for 2 postbaseline bone marrow assessments separated by at least 1 month would be considered progression, or 2) a doubling of the baseline absolute peripheral blood blast count that persists for at least 7 days and the final absolute peripheral blood blast count is > $10 \times 10^9/L$ . The date of progressive disease is defined as the first date that there was either a > 50% increase in bone marrow blast count from baseline, a persistence of bone marrow blasts > 70% in subjects with a baseline bone marrow blast count of > 70%, or a doubling of the peripheral blood blast count.

ANC = absolute neutrophil count

a If the pretreatment bone marrow blast percentage was 50% to 100%, the percentage of blasts must decrease to a value between 5% and 25%; if the pretreatment blast percentage was 20% to less than 49%, they must decrease by at least half to a value of more than 5%.

b Modification to IWG response criteria.

Notes: Deletions to the IWG response criteria are not shown.

Source: Cheson BD, Bennett JM, Kopecy KJ, et al. Revised Recommendations of the International Working Group for diagnosis, Standardization of response Criteria, Treatment Outcomes, and reporting Standards for Therapeutic Trials in Acute Myeloid Leukemia. J Clin Oncol 2003;21:4642-9.

CCI

CCI

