Censoring Rules for RFS		
Relapse	If the first relapse is a scheduled assessment then Date of first relapse; If the first relapse is an unscheduled assessment and no previous assessment, then Date of relapse; If the first relapse is an unscheduled assessment and has previous assessment, then Date of previous assessment (regardless of the response type).	Event
Death between scheduled assessments or within the first two missed scheduled assessments	Date of death	Event
No relapse	Date of last adequate assessment with evidence of no relapse	Censored
Death or progression after two or more missed scheduled assessments	Date of last adequate assessment with evidence of no relapse; if no adequate assessment exists then censored at date of first dose	Censored
Censoring Rules for PFS (sensitivity analysis), DoR and RFS		
Additional therapy received prior to progression or death	Date of additional systemic anticancer therapy	Censored

Censoring Rules for TTR		
Subject responded before PD	First documented response date (CR, PR, mCr, or HI for mDS Cohort, CR or CRi for AML Cohort)	Event
Subject responded after PD	Date of last adequate disease assessment at PD date or death date	Censored
Other case	Date of last adequate disease assessment; if no adequate assessment exists, then censored at date of first dose	Censored

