Partial Remission (PR)	
 ▪ One of the following BM Blasts values met: 
 ▪ BM blasts of 5% to 25% (inclusive) when baseline BM blasts is 50% to 100% (inclusive) ▪ BM blasts $\geq 5\%$ and 50% decrease from baseline when baseline BM blasts is $\leq 49\%$ (inclusive) 
AND
 
 ▪ All of the following peripheral blood values met: 
 ▪ Platelets $\geq 100 \times 10^9/L$ ▪ ANC $\geq 1.0 \times 10^9/L$ 
Where the date of the hematology assessment used is within the window -8 and +8 days of BM date. If multiple hematology assessments within this window, the closest to BM date should be used. If multiple on same distance to BM date, the one before BM date should be used

Relapse after CR or CRi	
 ▪ $> 5\%$ blast in peripheral blood following CR or CRi 
OR
 
$> 15\%$ BM blast following CR or CRi

Treatment Failure	
 ▪ Death w/death date during Cycle 1 
OR
 
 • Death w/death date ≤ 28 days after last dose date and prior to C2D1

Category	Definition
Progressive Disease^b	
 ▪ If the lowest/best response %BM blast is $\leq 70\%$, PD is defined when there's an increase of %BM blast of at least 50%. 
If the lowest/best response %BM blast is $> 70\%$ instead, PD is defined when there's an increase of %BM blast of at least 10% (absolute increase). If %BM blast doesn't increase more than 10%, PD is defined as an increase of at least 2x in %PB blast from the lowest/best response with %PB blast $> 10\%$.

Stable disease	
 ▪ Any evaluable time point where criteria for all other response categories (i.e., CR, CRi, PR, PD, Treatment failure, Not Assessable) are not met

ANC = absolute neutrophil count

^a If the pretreatment bone marrow blast percentage was 50% to 100%, the percentage of blasts must decrease to a value between 5% and 25%; if the pretreatment blast percentage was 20% to less than 49%, they must decrease by at least half to a value of more than 5%.

^b Modification to IWG response criteria.

Notes: Deletions to the IWG response criteria are not shown.

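### SAP Section 17.3 does not implement the peripheral-blood limb of AML progression in Protocol Appendix K; the main effect is that some protocol-defined progressions are labelled stable disease

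*SAP*

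**What the plan says.** Protocol Appendix K (Progressive Disease row) gives two alternative routes to AML progression, joined by 'or'. One uses marrow blasts. The other uses blood only: "a doubling of the baseline absolute peripheral blood blast count that persists for at least 7 days and the final absolute peripheral blood blast count" exceeds 10 × 10^9/L. Nothing in the row ties the blood route to a marrow level. For this route, progression is dated at the first doubling.

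SAP Section 17.3, under the same table title, first splits subjects by the lowest marrow blast percentage reached. At 70% or below, "PD is defined when there's an increase of %BM blast of at least 50" percent, and blood is not mentioned. Above 70%, the marrow rule becomes an absolute rise of at least 10 points. The blood rule then opens with the condition "If %BM blast doesn't increase more than 10" percent, and continues: "PD is defined as an increase of at least 2x in %PB blast from the lowest/best response with %PB blast" above 10%.

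The inputs for an absolute count are already collected. The central panel in Protocol Section 6.6.6.1 includes "White blood cell (WBC) count with differential", and percent blasts is one of its items.

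**The concern.** Protocol Section 6.7.1 says that response is derived by program from central laboratory results, so the SAP table is what will be run. If its blood rule is not the protocol's rule, derived progression depends on which document the programmer follows.

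Derived progression matters in three places. In SAP Section 17.3, stable disease is the residual category, so a progression that is not recognised at an evaluable time point becomes SD. In SAP Section 10.1, best overall response counts only what precedes progression. In SAP Table 4, the time-to-response row "Subject responded after PD" is censored. Routine marrows come every third cycle and at discontinuation, whereas blood counts are taken at least twice per cycle. Blood is therefore the more frequent evidence between marrows.

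**Working it through.** The plan gives no figure to reproduce here. The check sets the two rules side by side and applies them to illustrative subjects. All subject values are assumptions, because the documents give no distribution of white cell or blast counts.

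**Step 1: the rules compared.**

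| Feature | Protocol Appendix K | SAP Section 17.3 |
|---|---|---|
| Measure and threshold | absolute count, > 10 × 10^9/L | percent of white cells, > 10% |
| Reference for doubling | baseline | lowest/best value |
| Persistence | at least 7 days | none |
| Marrow condition | none | lowest marrow > 70%, on the natural reading |

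**Step 2: scale.** Absolute blasts = WBC × percent blasts / 100. At exactly 10% blasts:
- WBC 2: 0.2 × 10^9/L, which is 10 / 0.2 = 50 times below the protocol limit.
- WBC 5: 0.5 × 10^9/L, 20 times below.
- WBC 15 (the AML entry cap, exclusion criterion 34): 1.5 × 10^9/L, about 6.7 times below.
- WBC 100: 10 × 10^9/L. The two thresholds meet only here.

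**Step 3: missed, marrow at or below 70%.** Marrow goes from 40% to 45%. Baseline WBC is 8 with 25% blasts, so 8 × 0.25 = 2.0 × 10^9/L. Later WBC is 24 with 60% blasts for 10 days, so 24 × 0.60 = 14.4 × 10^9/L.
- Protocol: 14.4 / 2.0 = 7.2-fold, above 10 × 10^9/L, lasting more than 7 days. Progression.
- SAP: a 50% rise from 40% needs 60% marrow blasts, and 45% falls short. This branch has no blood rule. Not progression, hence SD.

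**Step 4: missed, marrow above 70%.** Marrow stays at 75%. Blood blasts stay at 60% while WBC rises from 8 to 20 for 10 days: 4.8 to 12.0 × 10^9/L.
- Protocol blood limb: 12.0 / 4.8 = 2.5-fold, above 10 × 10^9/L, sustained. Progression.
- SAP: the percentage has not doubled. Not progression. A lowest value above 50% can never double, since 2 × 50% = 100%.

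**Step 5: called early.** Baseline marrow is 80% and the first postbaseline marrow 72%. Blood blasts go from 6% to 12% at WBC 4: 0.24 to 0.48 × 10^9/L.
- SAP: lowest marrow above 70%, percentage doubled and above 10%. Progression at once.
- Protocol: the blood limb is not met. With baseline marrow above 70%, its marrow limb needs a second postbaseline value above 70% at least 1 month later.

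**Step 6: which endpoints can move.**
- Best overall response: SD ranks above PD. The label changes if the missed progression was the first evaluable outcome; an earlier SD would already outrank PD.
- Time to response: the censoring date moves. A response after a missed progression counts as an event instead of being censored. For an early call to cut off a response, every marrow so far must exceed 70% and the subject must later reach CR or CRi, which should be rare.
- AML duration of response: responders have marrow below 5%, so the > 70% branch cannot apply to them. Relapse already includes blood blasts above 5%. A count above 10 × 10^9/L is above 5% unless WBC reaches 10 / 0.05 = 200 × 10^9/L.
- Relapse-free survival: its events are relapse and death, so this limb does not enter.

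**The case against.** *The SAP may have changed the rule on purpose.* Its Progressive Disease row carries a footnote marking a modification to the IWG criteria, and Section 15 says that response derivations were updated. But Appendix K carries the same footnote on the same row, so it does not signal a further change. Section 15 speaks only of consistency with the IWG and modified IWG criteria. It names no change of unit, reference, persistence or scope.

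*The blood sentence might stand alone.* That is possible, although its 10% condition refers back to a rule that exists only in the > 70% branch. Read alone, it would catch the subject in Step 3, because blood blasts rose from 25% to 60%. It would still miss Step 4, and calls at low white counts would extend to every marrow level. Either way the wording needs correcting.

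*Blood outgrowth would prompt a marrow.* This is fair. Protocol Section 6.7.1 and footnote p of the Table of Events foresee marrow to confirm suspected progression. The gap in Step 3 does not need a missing marrow: a new marrow that has not risen by 50% leaves the subject SD.

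*Over-calling is small.* This stands. Where baseline and later marrows exceed 70%, the protocol's own marrow limb may call progression at the next scheduled marrow. The SAP then differs mainly in timing and confirmation.

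*The consequences are thin.* This largely stands. What remains is mostly an SD/PD label and a censoring date in AML subjects who do not respond. Investigator-assessed best response is reported as well (SAP Section 10.2).

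**Conclusion.** The two documents contradict each other on the blood limb of AML progression, and nothing in the SAP identifies or justifies the difference. The larger effect is missed progression where the lowest marrow is 70% or below; early or unconfirmed calls above 70% are the smaller one. This is a minor point. The number of subjects affected cannot be derived, and the examples rest on assumed values and on the natural reading of the SAP sentence.

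A reader might infer more than the documents support:
- That the primary ORR changes. As written, it is the proportion reaching CR or CRi; the cut-off at progression belongs to the best overall response summary.
- That AML duration of response or relapse-free survival changes. Step 6 shows that this limb does not affect them.
- That progression-free survival changes. It is an endpoint of the MDS cohort only.
- That the 20- to 50-fold threshold gap measures misclassification. It compares thresholds alone, and on the natural reading over-calling is confined to marrow above 70%.
- That efficacy evaluable or interim membership shifts. It depends on discontinuation for progression. SAP Section 6 takes discontinuation reasons from the CRF, and no passage ties them to derived progression.

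**What to change.** Reconcile SAP Section 17.3 with Protocol Appendix K. Write the blood limb as a separate 'OR' condition for all AML subjects, independent of marrow level:
- absolute blasts = WBC × percent blasts / 100, from the central panel;
- at least double the baseline count, above 10 × 10^9/L, and sustained for at least 7 days;
- progression dated at the first doubling, as in Appendix K.

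State how a baseline count of zero is handled, since doubling is then undefined; for example, the count and persistence conditions alone could apply. State also that the SAP's marrow rule refers to the lowest value while the blood rule refers to baseline, so that the mixture is explicit. If any of the four departures is intended, list it in SAP Section 15 with a reason.

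The cost is SAP wording and one derivation from data already collected. The downside is small: persistence sometimes depends on the next scheduled sample. Hematology is on Days 1, 8, 15 and 22 in Cycles 1 and 2 and on Days 1 and 15 afterwards, so samples are nominally 7 or 14 days apart, before visit windows.

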17.4. Revised International Prognostic Scoring System for MDS – IPSS-R (Greenberg, 2012)

IPSS-R Cytogenetic Risk Groups

Cytogenetic Prognostic Subgroups	Cytogenetic Abnormalities
Very good	-Y, del(11q)
Good	Normal, del(5q), del(12p), del(20q), double including del(5q)
Intermediate	del(7q), +8, +19, i(17q), any other single or double independent clones
Poor	-7, inv(3)/t(3q)/del(3q), double including -7/del(7q), Complex: 3 abnormalities
Very poor	Complex: > 3 abnormalities

IPSS-R Prognostic Score Values

Prognostic variable	0	0.5	1	1.5	2	3	4
Cytogenetics	Very Good	-	Good	-	Intermediate	Poor	Very Poor
Bone Marrow Blast (%)	≤ 2	-	> 2 - < 5	-	5 - 10	> 10	-
Hemoglobin (g/dL)	≥ 10	-	8 - < 10	< 8	-	-	-
Platelets (× 10 ⁹ /L)	≥ 100	50 - < 100	< 50	-	-	-	-
ANC (× 10 ⁹ /L)	≥ 0.8	< 0.8	-	-	-	-	-

ANC = absolute neutrophil count

The total IPSS-R score is calculated as the sum of the cytogenetics, bone marrow blast percentage, hemoglobin, platelets and ANC individual scores.

IPSS-R Prognostic Risk Categories/Scores

Risk Category	Risk Score
Very Low	≤ 1.5
Low	$> 1.5 - 3$
Intermediate	$> 3 - 4.5$
High	$> 4.5 - 6$
Very High	> 6

IPSS-R: Prognostic Risk Category Clinical Outcomes

Prognostic variable	No. pts	Very Low	Low	Intermediate	High	Very High
Patients (%)	7012	19%	38%	20%	13%	10%
Median Overall Survival (years)	-	8.8	5.3	3.0	1.6	0.8
Median time to 25% AML evolution	-	Not reached	10.8	3.2	1.4	0.7

Source: Greenberg, Tuechler H, Schanz J, Sanz G, Garcia-Manero G, Solé F, et al. Revised international prognostic scoring system for myelodysplastic syndrome. Blood. 2012;120(12):2454-65

17.5. Risk Status Based on Cytogenetics for Acute Myeloid Leukemia

Risk Groups

Risk Status	Cytogenetics	Molecular Abnormalities ^a
Better-risk	inv(16) ^{b, c} t(16;16) ^b t(8;21) ^b t(15;17)	Normal cytogenetics: NPM1 mutation in the absence of FLT3-ITD or isolated biallelic CEBPA mutation
Intermediate-risk	Normal cytogenetics +8 t(9;11) Other non-defined	t(8;21), inv(16), t(16;16): with c-KIT ^d mutation
Poor-risk	Complex (≥ 3 clonal chromosomal abnormalities) Monosomal karyotype -5, 5q-, -7, 7q- 11q23 - non t(9;11) inv(3), t(3;3) t(6;9) t(9;22) ^e	Normal cytogenetics: with FLT3-ITD mutation ^f

^a The molecular abnormalities included in this table reflect those for which validated assays are available in standardized commercial laboratories. Given the rapidly evolving field, risk stratification should be modified based on continuous evaluation of research data. Other novel genetic mutations have been identified that may have prognostic significance.

^b Other cytogenetic abnormalities in addition to these findings do not alter risk status.

^c Paschka P, Du J, Schlenk RF, Gaidzik VI, Bullinger L, Corbacioglu A, et al. Secondary genetic lesions in acute myeloid leukemia with inv(16) or t(16;16): a study of the German-Austrian AML study group (AMLSG). Blood 2013; 121:170-177.

^d Emerging data indicates the presence of c-KIT mutation in subjects with t(8;21), and to a lesser extent, inv(16), confers a high risk of relapse. These subjects should be considered for clinical trials, if available.

^e For Philadelphia+ acute myeloid leukemia (AML) t(9;22), manage as myeloid blast crisis in chronic myeloid leukemia (CML), with addition of tyrosine kinase inhibitors. These subjects are excluded from study entry.

^f FLT3-ITD mutations are considered to confer a significant poor outcome in subjects with normal karyotype, and these subjects should be considered for clinical trials where available. There is controversy as whether FLT3-TKD mutations carry equally poor prognosis

Source: National Comprehensive Cancer Network Clinical Practice Guidelines in Oncology for Acute Myeloid Leukemia. National Comprehensive Cancer Network website. Available at http://www.nccn.org/professionals/physician_gls/PDF/aml.pdf. Accessed 05 Aug 2015.

CCI

CCI
